4.4 Endpoints

4.4.1 Primary Endpoints

- 4.4.1.1 To determine if 50 mg/day Modafinil decreases freezing of gait in PD patients with FOG compared with placebo as measured by the Giladi Freezing of gait questionnaire (FOG-Q) after 12 weeks of active treatment or placebo. Subjects who drop out of the study after at least 6 weeks of either treatment arm will be included in this analysis.
- 4.4.1.2 To determine if 50 mg/day Modafinil decreased the decline stride length seen in PD patients with FOG. The rate of decline in stride length will be compared plotting the stride length at steady state in subjects in the early and late-start arms to determine if the rate of decline improves in subjects taking Modafinil in the early-start arm and whether this rate of decline also improves in the second phase of the trial in the delayed-start arm.

We will also determine if at the completion of 24 weeks, the early-start arm has differential change in slope of other continuous gait parameters (stride width, gait cycle time, gait cycle velocity, swing and stance percent, total single and double support time, cadence) compared to the delayed start arm suggesting that Modafinil slows the progression of the gait decline.

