10.0 STATISTICAL CONSIDERATIONS

The study is a prospective repeated measures longitudinal design. The primary outcome response is the FOG-Q total score and the stride length changes, and the secondary responses are the UPDRS Part III subscale, the PDQ-39, the RBD scale, and the Epworth Sleepiness Scale. These measures will be observed at 6 time points for both study arms. A primary statistical goal is to estimate the mean response at all six time points for each group and subsequently estimate changes in the outcome measures for each study group from baseline. Additionally, it is of interest to estimate the how the study groups differ in their mean change from baseline. A two group repeated measures linear model will be employed to determine significance for within each group and then to compare among the groups. Significance will be declared at the 5% level of significance and Bonferroni methods will be used for multiple comparisons. This analysis approach will be applied to the primary and secondary responses.

The study calls for 10 subjects in both arms for a total of 20 patients. Within a study arm the linear model will have in excess of 80% power to detect a 1.75 unit difference in observed means. Based on standard deviation estimates from previous researchers in similar settings,²² the FOGQ (the primary response) has a standard deviation of 3.58. This implies that we will have power to detect a 6.265 (1.75*3.58) unit difference among time point means at the 5% level of significance. Power calculations are from 'Tables of Sample Sizes in the Analysis of Variance' published by Bratcher.²³

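### The Bonferroni family is not defined across the two primary responses, and eight further gait slopes under Primary Endpoints carry an efficacy inference that no stated error rule covers.

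*Combined protocol and SAP*

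**What the plan says.** Section 10 defines the primary outcome in the singular but gives it two parts: "The primary outcome response is the FOG-Q total score and the stride length changes". Two sentences describe the analysis and its error control: "A two group repeated measures linear model will be employed to determine significance for within each group and then to compare among the groups", and then "Significance will be declared at the 5% level of significance and Bonferroni methods will be used for multiple comparisons". The scope is given next: "This analysis approach will be applied to the primary and secondary responses". The secondary responses listed there are UPDRS Part III, PDQ-39, the RBD scale and the Epworth scale. The power paragraph refers to only one primary ("the FOGQ (the primary response) has a standard deviation of 3.58") and uses the full 5%.

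Section 4.4.1 numbers two primary endpoints: FOG-Q after 12 weeks (4.4.1.1) and the rate of decline in stride length (4.4.1.2). A further unnumbered paragraph under the same heading says "We will also determine if at the completion of 24 weeks, the early-start arm has differential change in slope of other continuous gait parameters". It lists stride width, gait cycle time, gait cycle velocity, swing percent, stance percent, single support time, double support time and cadence. It describes a difference between arms as "suggesting that Modafinil slows the progression of the gait decline".

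The protocol does have an exploratory tier (4.3 and 4.4.3). It holds only cognitive measures.

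**The concern.** There are two gaps.

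The first is the undefined family. The Bonferroni sentence directly follows a model that makes many comparisons inside one response: six time points, within each arm and then between arms. The likelier reading is that the correction belongs there. Nothing says that it also divides the 5% between FOG-Q and stride length, or whether one or both must succeed. The undivided 5% in the power statement fits the narrower reading.

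The second gap is larger. The eight extra slopes sit under the primary heading and come with a conclusion about slowing progression, yet they are outside the set of responses to which section 10 applies its rule. With 10 subjects per arm, one chance difference in one gait parameter could be reported under a primary heading as evidence that the drug slows decline. The 5% that the plan declares would then not describe the error rate of its conclusion.

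**Working it through.** **Inputs.** Section 10: 5% significance level, two primary responses, 10 subjects per arm, six time points, a standardised difference of 1.75 and an FOG-Q SD of 3.58. Section 4.4.1: eight further gait parameters. The documents give no correlations between measures, so those below are assumptions.

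**1. The plan's own figure.** 1.75 × 3.58 = 6.265 points, as stated. For a one-way layout with 6 means, 10 per mean and a largest difference of 1.75 SD, the non-centrality is 10 × 1.75² / 2 = 15.31 with 5 and 54 degrees of freedom. Power at 5% is 83.4%, which agrees with the claim of more than 80%. It is reached with the whole 5% spent on one response.

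**2. Two primaries, each at 5% (Bonferroni only within a response).** If independent, 1 − 0.95² = 9.75%. With assumed correlation 0.5 it is 9.1%, and with 0.9 it is 7.0%. If Bonferroni does span the two, 1 − 0.975² = 4.9% if independent, and never more than 5%.

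**3. The eight further slopes, each at 5% (assumed, because no level is stated for them).** If independent, 1 − 0.95⁸ = 33.7%. With equal correlation 0.5 it is 25%, and with 0.8 it is 16%.

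**4. All ten.**

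| Assumption | At least one false result |
|---|---|
| Independent: 1 − 0.95¹⁰ | 40.1% |
| Equal correlation 0.5 | 29% |
| Equal correlation 0.8 | 17% |
| Equal correlation 0.9 | 13% |
| Independent, favourable direction only: 1 − 0.975¹⁰ | 22.4% |
| Independent, swing and stance percent counted once: 1 − 0.95⁹ | 37.0% |

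**5. Which gap matters more.** If the two primaries shared the 5% and the eight slopes stayed at 5% each, the rate if independent would still be 1 − 0.975² × 0.95⁸ = 36.9%. Correcting the primaries alone barely changes the total.

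**6. Cost of dividing the 5%.** With 2.5% in step 1, within-arm power at 1.75 SD falls from 83.4% to 74.7%. Regaining 80% takes 11 per arm or a difference of 1.84 SD (1.84 × 3.58 = 6.59 points). For a simple two-sample t test between arms with 10 each, the difference detectable with 80% power rises from 1.325 SD (4.74 points) to 1.484 SD (5.31 points). The point values assume that the SD of 3.58 also applies to that contrast.

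**The case against.** The strongest reply is that the plan does promise Bonferroni and does not restrict it to time points. If it spans the responses, the two primaries are controlled at 5% or below. That stands. A reader might infer that each primary is tested at 5% with no correction, but section 10 does not say so. What the text supports is an undefined family.

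For the eight slopes, the 5% level and Bonferroni stand in the same sentence with the same scope. If silence in section 10 means that no correction reaches the slopes, it equally means that no 5% test is stated for them. This also stands, and it is why the 34% and 40% figures are conditional. It does not close the gap: an efficacy reading is attached to a difference, and the plan gives no standard by which a difference would be declared.

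There are also signs that the slopes were meant as additional. They are unnumbered, absent from the primary objectives in 4.1 and from section 10, and introduced as something also to be examined. Their inference is worded as a suggestion. Against that are the heading they stand under and the existence of an exploratory tier where they were not placed.

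A reader might also take 40% as the trial's error rate. It is an upper figure that assumes independence, no correction and errors in either direction. The gait measures come from the same walks, and swing and stance percent are complementary shares of one cycle, so independence is not realistic.

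Finally, this is a pilot with estimation as a stated goal. That lowers the consequence, but the plan still declares significance and lists efficacy among its objectives.

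**Conclusion.** The point holds in two parts. For FOG-Q and stride length, the Bonferroni family and the success rule are unstated. If the correction acts only within a response, the chance of at least one false primary result is up to about 10%; if it spans both, it is at most 5%. For the eight further gait slopes, the plan allows a progression claim under a primary heading with no stated error control. Adding them at an assumed 5% each gives up to about 40% across ten tests if independent, about 29% at correlation 0.5 and about 17% at 0.8, or about 22% for favourable errors only if independent. All of these rest on the assumed test level, and the intermediate ones on assumed correlations. The documents do not support the flat statement that the error rate is 10% to 40%. The slopes are the larger part of the problem and the cheaper one to resolve.

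**What to change.** 1. Move the eight other gait slopes from 4.4.1 to 4.4.3. Report them as estimates with 95% intervals, and delete the inference about slowing progression for them.

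2. In section 10, state that the Holm step-down at an overall two-sided 5% applies across one prespecified between-arm contrast per primary: the week-12 change for FOG-Q, and the between-arm difference in rate of decline for stride length. The second keeps the endpoint as 4.4.1.2 defines it. A week-12 stride-length contrast would replace that endpoint with a different one.

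3. Say separately which comparisons within a response Bonferroni covers.

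No new data or visits are needed. The costs are real but small. At least one primary must reach 2.5%. If the 5% is undivided at present, this lowers within-arm power at 1.75 SD from about 83% to about 75% for a response judged at that level. If Bonferroni already spans the two primaries, Holm costs nothing, since it is never less powerful. The gait slopes can no longer support a confirmatory claim.

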2.0 STUDY SUMMARY

Title	Modafinil as a novel therapy for the treatment of freezing of gait in Parkinson's disease			
Short Title	Modafinil for FOG			
Protocol Number	MODFOG01			
Phase	Pilot, feasibility			
Methodology	Randomized, placebo-controlled delayed start			
Study Duration	1 year			
Study Center(s)	Single-center			
Objectives	Safety and efficacy of Modafinil for the treatment of freezing of gait in Parkinson's disease			
Number of Subjects	Enrolling 25 for a total of 20			
Diagnosis and Main Inclusion Criteria	Idiopathic Parkinson disease with freezing of gait on stable Parkinson disease treatment for 3 months.			
Study Product(s), Dose, Route, Regimen	Modafinil 50 mg capsule oral daily, Placebo capsule oral daily			
Duration of administration	24 weeks (early-start), 12 weeks (delayed-start)			
Reference therapy	none			
Statistical Methodology	The study is a prospective repeated measures longitudinal design. A primary statistical goal is to estimate the mean response at all six time points for each group and subsequently estimate changes in the outcome measures for each study group from baseline.			

PI: [name], PhD

Sponsor: UAMS

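### Holm's step-down version of the Bonferroni correction named in Section 10.0 would keep the 5% familywise error, never reject less and sometimes reject more: a cheap efficiency gain, not the repair of an error

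*Combined protocol and SAP*

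**What the plan says.** The multiplicity rule is one sentence in Section 10.0: "Significance will be declared at the 5% level of significance and Bonferroni methods will be used for multiple comparisons". It does not say whether the correction is single-step or step-down, and it does not say which comparisons form a family.

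The same section describes a lot of testing. On outcomes: "The primary outcome response is the FOG-Q total score and the stride length changes". Four further measures come after these two: "the secondary responses are the UPDRS Part III subscale, the PDQ-39, the RBD scale, and the Epworth Sleepiness Scale". On visits: "These measures will be observed at 6 time points for both study arms". On the model: "A two group repeated measures linear model will be employed to determine significance for within each group and then to compare among the groups". On scope: "This analysis approach will be applied to the primary and secondary responses".

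Estimation is also an aim: "A primary statistical goal is to estimate the mean response at all six time points for each group". The Study Summary (Section 2.0) repeats this and adds the intention to "subsequently estimate changes in the outcome measures for each study group from baseline".

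**The concern.** Read in the ordinary way, a Bonferroni correction holds every comparison to 5%/m, even after others in the family have been rejected. Holm relaxes the threshold as rejections accumulate and keeps the same 5% bound. With two primary responses, four secondary responses, six visits and only 10 subjects per arm, several comparisons may reflect real effects at once. That is the situation in which the single-step rule can miss a true change that an equally strict procedure would declare. What is at stake is power for individual comparisons. No error rate is at risk.

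**Working it through.** **1. The plan's own figure.** Section 10.0 claims more than 80% power within an arm for a difference of 1.75 SD. Take a one-way ANOVA with 6 means, n = 10 and a largest difference of 1.75 SD. The noncentrality is 10 × 1.75²/2 = 15.31. With 5 and 54 degrees of freedom at 5%, power is 83.4% (82.5% with repeated-measures error df of 45). With n = 9 it is 78.0%. Also 1.75 × 3.58 = 6.265. The figure reproduces, but it is an overall test at an unadjusted 5%, so it says nothing about the cost of any correction.

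**2. Why Holm never rejects less.** Order the p-values p(1) ≤ … ≤ p(m).
- Bonferroni rejects those at or below 0.05/m.
- Holm compares p(1) with 0.05/m, p(2) with 0.05/(m−1), and so on, stopping at the first failure. Every threshold is at least 0.05/m, so all Bonferroni rejections are kept.
- The first step is identical, so the event of at least one rejection is identical.
- Error control: if m0 null hypotheses are true, the first of them to be rejected meets a threshold of at most 0.05/m0. The chance of any false rejection is then at most m0 × 0.05/m0 = 0.05, whatever the dependence.

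**3. Two primaries (m = 2).** For independent tests, the gain per test is [power(0.05) − power(0.025)] × power of the other test at 0.025. The unadjusted power and the correlations are assumptions, because the documents give no stride-length effect or SD, no endpoint correlation and no between-arm power.
- Both effects real, 80% unadjusted each: Bonferroni 71.2%. Gain (0.800 − 0.712) × 0.712 = 6.2 points, so Holm gives 77.5%. At correlation 0.5 the gain is 5.2 points; at 0.8 it is 4.4.
- Power for both, independent: 0.712² = 50.7% under Bonferroni; 0.800² − 0.088² = 63.2% under Holm. Power for at least one: 1 − 0.288² = 91.7% under either.
- Only one effect real: (0.800 − 0.712) × 0.025 = 0.2 points.
- Both at the plan's 1.75 SD, 10 v 10 t-test: 95.9% unadjusted, 91.8% at 0.025. Gain (0.959 − 0.918) × 0.918 = 3.8 points.
- Both at 3/3.58 = 0.84 SD (an assumed 3-point effect), 10 v 10: 43% unadjusted, 31% at 0.025. Gain (0.426 − 0.310) × 0.310 = 3.6 points.

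**4. Five changes from baseline in one arm (m = 5).** Paired t-tests by simulation, n = 10, the plan's SD of 3.58, no effect at week 26. The within-subject correlation is assumed. The entries are Holm minus Bonferroni in power per truly changed visit, in percentage points to the nearest half point.

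| Assumed true drop in FOG-Q | corr. 0.3 | 0.5 | 0.7 | 0.8 |
|---|---|---|---|---|
| 3 points, weeks 6–24 | 4 | 6 | 9 | 8 |
| 3 points, weeks 18 and 24 only | 1 | 1.5 | 2.5 | 2.5 |
| 3 points, one visit only | 0 | 0 | 0 | 0 |
| 2.4 points, weeks 6–24 | 2 | 3.5 | 6.5 | 9 |
| 6.265 points, weeks 6–24 | 6 | 2 | 0 | 0 |

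In the first row, power per visit goes from 34% to 40%, 59% to 68% and 80% to 88% at correlations 0.5, 0.7 and 0.8. The second row is the pattern a drug effect would give in the delayed-start arm, which takes placebo to week 12 (Section 6.2). The fourth row uses 10% of the 24-point scale, one reading of the target in Section 8.1.1.

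**5. Larger families, every effect real, 80% unadjusted power each.** At correlations 0 and 0.5:
- m = 5: 58.9% to 70.4% (+11.5) and 59.0% to 68.8% (+9.9, from unrounded values).
- m = 6: 56.5% to 68.3% (+11.8) and 56.4% to 66.7% (+10.3).
- At 50% unadjusted power, m = 5 or 6 gives only about +3.5 to +5.8.

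**6. Error rates.** With no effect at any visit, the familywise error in step 4 was the same for both methods, 4.3% to 4.6%. With a 3-point drop at weeks 6–24, false rejection at week 26 rose from about 1% under Bonferroni to about 2% to 4% under Holm. Holm uses more of the 5% allowance but does not exceed it.

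**The case against.** Four points can fairly be made in defence of the plan.

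*The text does not say single-step.* A reader might infer that Section 10.0 commits to testing at 5%/m. That is the usual meaning, but the wording is a general plural and could cover a step-down version. This stands. If Holm was intended, naming it removes the doubt before data are seen.

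*The gain has no single size.* A reader might infer that this trial gives up a set amount, say 5 to 9 points. The documents do not support that. They fix no family, no correlations and no number of real effects, and the cases above run from 0 to about 12 points. Holm also adds nothing to the chance of finding at least one effect, which matters in a pilot looking for any signal. This stands in full.

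*Bonferroni buys something.* Its simultaneous confidence intervals match its tests. Holm has no equally simple intervals, and estimation is a stated goal. A reader might infer that the power is lost for nothing, and that goes too far: Bonferroni is dominated for testing only. Still, Section 10.0 also declares significance, and the intervals can be kept alongside Holm.

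*The undefined family is the larger gap in Section 10.0.* True, but separate. Whichever family is chosen, Holm rejects at least as much at the same error bound.

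**Conclusion.** The point holds as an optional efficiency improvement. For significance declarations, Holm controls the familywise error at 5% with no assumptions beyond those of Bonferroni and never rejects less. That part is a theorem and needs no input from the trial.

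The size does rest on assumptions. Per comparison, the gain is about 0 with one real effect, 1 to 6 points in many plausible cases, and roughly 9 to 12 points with five or six comparisons, most or all of them real and reasonably well powered. It is zero for at least one rejection. Two-sided tests were assumed, since sidedness is not stated.

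The plan is not wrong on this point. Bonferroni is valid and conservative, and no estimate, error rate or safety conclusion is compromised by keeping it.

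**What to change.** In Section 10.0, replace the reference to Bonferroni methods with a statement that the Holm (step-down Bonferroni) procedure is used for multiple comparisons. Keep Bonferroni-adjusted simultaneous confidence intervals for the estimated means and changes.

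The cost is one phrase: no new data, no extra assumptions and no loss of the 5% familywise bound. The drawback to state in the plan is that a Bonferroni-adjusted interval may include zero for a comparison that Holm declares significant. The text should say in advance that the Holm result decides significance.

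### The stated detectable FOG-Q difference of 6.265 points leaves out within-subject correlation, so it does not describe the planned within-arm repeated measures test; it is generally conservative, by an amount the documents do not fix

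*Combined protocol and SAP*

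**What the plan says.** Section 10.0 describes the design and model in these terms: "The study is a prospective repeated measures longitudinal design"; "These measures will be observed at 6 time points for both study arms"; "A two group repeated measures linear model will be employed to determine significance for within each group and then to compare among the groups". On multiplicity it says: "Significance will be declared at the 5% level of significance and Bonferroni methods will be used for multiple comparisons". It does not give the number of comparisons.

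The sample size paragraph of the same section states "The study calls for 10 subjects in both arms for a total of 20 patients" and then "Within a study arm the linear model will have in excess of 80% power to detect a 1.75 unit difference in observed means". The only variance input is that "the FOGQ (the primary response) has a standard deviation of 3.58", taken from a cited study. The result is "This implies that we will have power to detect a 6.265 (1.75*3.58) unit difference among time point means at the 5% level of significance". The source given for the power is a set of published ANOVA sample-size tables. The section does not report which table entry was used, a within-subject correlation, an SD of change or a residual SD.

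**The concern.** Visit means within an arm come from the same ten people. The error in a difference between two such means depends on the within-subject SD, which under equal correlation is the score SD times sqrt(1 − rho). A calculation for that contrast needs rho, the SD of change or the residual SD, and Section 10 supplies none of them. The figure looks like a calculation for six separate groups of ten people.

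This is the only quantitative justification for 10 per arm, so within-arm changes and null results are likely to be read against it. Section 8.1.1 looks for a 10% change in FOG-Q. If that means 10% of the 24-point maximum (the base is not stated), it is 2.4 points, and 6.265 is 6.265 / 2.4 = 2.6 times as large. Whether the within-arm analysis can come near that target depends largely on the correlation that the plan omits.

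**Working it through.** **Inputs from Section 10.0:** n = 10 per arm, k = 6 visits, alpha = 0.05, standardized difference tau = 1.75, score SD = 3.58. **Assumed, because not stated:** rho from 0.3 to 0.8 (0 as the limiting case), compound symmetry, ten subjects with all six visits, two-sided t tests, and the least favourable pattern of means for the F test (only the two extreme means differ).

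**Step 1: reproduce the plan's figure.** 1.75 × 3.58 = 6.265, which is exact. For a one-way ANOVA of k independent groups, the noncentrality is lambda = n·tau²/2, with k − 1 and k(n − 1) df.

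- n = 10, k = 6: lambda = 10 × 1.75² / 2 = 15.31, df 5 and 54, power 83.4%.
- n = 9, k = 6: power 78.0%.

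Ten is thus the smallest group size above 80% for six independent groups, which agrees with the stated n and the stated power. With k = 2 to 5, 7 to 9 per group would be enough; k = 8 needs 11. Only k = 7 also gives 10 (80.9%), and the study has six visits. The match is close, but k = 6 remains an inference.

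**Step 2: overall F test with the same subjects at each visit.** lambda = n·tau² / (2(1 − rho)), df 5 and 45. Solving for 80% power gives tau = 1.70, 1.42, 1.20, 0.93 and 0.76 at rho 0, 0.3, 0.5, 0.7 and 0.8. Multiplying the unrounded tau by 3.58 gives the points in the table. Power at 6.265 points is 82.5%, 94.5% and 99.1% at rho 0, 0.3 and 0.5, and above 99.9% from rho 0.7.

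**Step 3: paired comparisons under the plan's Bonferroni rule.** The SD of change is 3.58 × sqrt(2(1 − rho)), and the paired t test has 9 df. The test level is 0.05/5 = 0.01 for five comparisons with baseline, or 0.05/15 = 0.0033 for all pairs of visits.

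| rho | F test, points (6.265 ÷ this) | Bonferroni, 5 vs baseline | Bonferroni, all 15 pairs |
|---|---|---|---|
| 0 | 6.09 (1.03) | 6.74 (0.93) | 7.98 (0.79) |
| 0.3 | 5.10 (1.23) | 5.64 (1.11) | 6.68 (0.94) |
| 0.5 | 4.31 (1.45) | 4.77 (1.31) | 5.64 (1.11) |
| 0.7 | 3.34 (1.88) | 3.69 (1.70) | 4.37 (1.43) |
| 0.8 | 2.72 (2.30) | 3.02 (2.08) | 3.57 (1.76) |

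A ratio below 1 means that the planned comparison needs more than 6.265 points.

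**Step 4: departure from sphericity.** With a Greenhouse-Geisser epsilon of 0.7, the F test detects 4.90 points at rho 0.5 and 3.10 at rho 0.8. With epsilon 0.5 it detects 6.58 at rho 0.3, 5.56 at rho 0.5 and 3.52 at rho 0.8.

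**The case against.** The strongest reply is that the plan claims only that power exceeds 80% at 1.75 SD. Under the unadjusted F test with sphericity, that holds at every non-negative rho, starting from 82.5% at rho 0. The multiplication is exact, and an independent-groups figure can be defended as a cautious bound for a pilot. This stands: with that test, the plan does not overclaim power.

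Three stronger readings are tempting, and the documents do not support them.

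- A reader might infer that Section 10 says changes below 6.3 points cannot be detected. It does not. It gives a lower bound on power at one difference.
- A reader might infer that the figure is too large by a fixed factor, such as 1.5 to 2.3. That range needs an assumed rho of 0.5 to 0.8, sphericity and no multiplicity adjustment. Nothing in the documents sets a floor of 0.5. Entry requires FOG-Q above 8 (Section 5.1), which restricts the range of scores and can lower the correlation. The switch from placebo to active drug and the washout (Section 6.2) make compound symmetry doubtful in the delayed-start arm.
- A reader might infer that the F-test column can simply replace 6.265. That would ignore the Bonferroni rule in the same section and would put optimistic figures in place of a cautious one.

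Two points also rest on inference. The table entry k = 6 is not stated. Section 10 also does not say whether 3.58 is a between-subject or a residual SD. If it were a within-subject residual SD, 6.265 would be about right (82.5% power). The text, however, presents it only as the SD of the FOG-Q.

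What the reply does not answer is that a repeated measures power figure needs a correlation or an SD of change, and the plan states neither.

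**Conclusion.** The point holds in a limited form. The 6.265-point figure does not describe the planned within-arm test. It matches six independent groups of ten, while the plan compares six visits of the same ten subjects. When visits are clearly correlated it is generally conservative. Over rho 0.5 to 0.8 it exceeds the detectable difference by 1.45 to 2.30 times for the F test, 1.31 to 2.08 times with five Bonferroni comparisons, and 1.11 to 1.76 times with all 15 pairs. At rho 0.3 these ratios fall to 1.23, 1.11 and 0.94, so the direction can reverse. Low rho without sphericity has the same effect: 6.58 points at rho 0.3 and epsilon 0.5.

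All of these sizes rest on an assumed rho, on 3.58 being a score SD, and on ten complete subjects per arm. They concern within-arm change only. They say nothing about the comparison with placebo at 12 weeks in Section 4.4.1.1, for which Section 10 gives no power.

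**What to change.** In Section 10.0, replace the 6.265-point statement with a repeated measures calculation that does the following:

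- states the rho or SD of change assumed, and what the 3.58 represents;
- states the number of Bonferroni comparisons;
- tabulates the detectable within-arm change over rho 0.3 to 0.8 with that adjustment (for five comparisons with baseline: 5.6, 4.8, 3.7 and 3.0 points at rho 0.3, 0.5, 0.7 and 0.8);
- says what allowance is made for departure from sphericity;
- labels the figures as dependent on an assumed rho.

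The existing gait cohort described in Sections 3.3 and 5.4 could supply rho if it holds repeated FOG-Q scores; the documents do not say whether it does. The cost is rewording one paragraph. No change to the design or the sample size follows from this point.
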